A subject who does not show evidence of disease progression may continue receiving GS-5829 once daily and exemestane (Group A) or fulvestrant (Group B) until disease progression (clinical or radiographic), unacceptable toxicity, withdrawal of consent, or death whichever comes first.

Following treatment discontinuation, subjects will be followed for safety for 30 days from the last dose of study drug. Pharmacokinetic and pharmacodynamic samples for GS-5829 will be collected on Day 1 and Day 15 of Cycle 1 at pre-dose, 0.5, 1, 2, 3, 4, 6, 8 and 24 hours post-dose and anytime on Day 1 of Cycles 2 through 6.

Randomized Phase 2 Dose Expansion

Sparse pharmacokinetics and pharmacodynamic samples will be collected at pre-dose and anytime between 1 to 4 hours post-dose on Day 1 and Day 15 of Cycle 1 and at pre-dose on Day 1 of Cycles 3 and 6. Note: pharmacokinetic samples will only be collected for subjects who are randomized to a GS-5829 in combination with fulvestrant arm (Arm 1).

Subjects in the Randomized Phase 2 Dose Expansion portion of the study will also be followed for up to two years for OS.

Test Product, Dose, and Mode of Administration:

GS-5829 will be supplied as round, plain-faced tablets containing 1 mg or 5 mg GS-5829. GS-5829 tablets will be self-administered orally once daily, beginning on C1D1 of the study and thereafter at approximately the same time each day until end of treatment (EOT).

For subjects in Group A of the Phase 1b Dose Escalation, 25 mg exemestane tablets will be self-administered orally once daily (or in accordance with locally approved labeling), beginning on C1D1 of the study and thereafter at approximately the same time each day until the EOT.

For subjects in Group B of the Phase 1b Dose Escalation or subjects in Arm 2 of the Randomized Phase 2 Dose Expansion, fulvestrant will be administered intramuscularly (in accordance with locally approved labeling) by the clinic staff approximately every 28 days (\pm 3 days) until the EOT.

For subjects in the Phase 1b Dose Escalation or subjects in the Randomized Phase 2 Dose Expansion part of the study for whom are treatment naïve (in metastatic setting) and for all subjects for whom C1D1 is the subject's first dose of fulvestrant, a one-time additional dose of 500mg fulvestrant will be administered on Cycle 1, Day 15 (\pm 3 days).

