Reference Therapy, Dose, and Mode of Administration:	
The reference therapy in the Randomized Phase 2 Dose Expansion portion of the study is fulvestrant alone.
 
For subjects in the Randomized Phase 2 Dose Expansion, fulvestrant will be administered intramuscularly (in accordance with locally approved labeling) by the clinic staff approximately every 28 days (± 3 days) until the EOT. For subjects in the dose expansion Phase whom are treatment naïve (in metastatic setting) and for all subjects in the dose escalation phase for whom C1D1 is the subject's first dose of fulvestrant, a one-time additional dose of 500 mg fulvestrant will be administered on Cycle 1 Day 15 (± 3 days).

Criteria for Evaluation:	Phase 1b Dose Escalation and Randomized Phase 2 Dose Expansion
Safety:	Safety will be evaluated by assessment of clinical laboratory tests, physical examination, 12-lead ECG, vital signs measurements, and the documentation of AEs
Efficacy:	
PFS – defined as the interval from date of randomization to the earlier of the first documented confirmed disease progression or death from any cause
 
ORR – defined as the proportion of subjects who achieve CR or PR, based on RECIST v. 1.1
 
CBR - defined as the proportion of subjects who achieve a CR or PR or SD that lasts for ≥ 24 weeks based on RECIST v. 1.1
 
OS - defined as interval from date of randomization to date of death from any cause

Pharmacokinetics:	Phase 1b Dose Escalation: The pharmacokinetic parameters for GS-5829 will be calculated as applicable: [e.g., C_{max} , and AUC_{tau}]
Statistical Methods:	
Analysis Methods
 
Phase 1b Dose Escalation: The incidence of DLTs, AEs, serious adverse events (SAEs), and clinically significant laboratory abnormalities in subjects treated with GS-5829 in combination with exemestane or fulvestrant will be evaluated.
 
Randomized Phase 2 Dose Expansion: The Intent-to-Treat (ITT) analysis set includes all subjects who are randomized, regardless of whether subjects receive any study drug(s) or receive a different regimen from the regimen they were randomized to. Treatment assignment will be designated according to randomization. The analysis of PFS based on the ITT analysis set will be considered the primary analysis of the study. PFS will also be analyzed for each of the 2 strata separately.

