4.2. Inclusion Criteria

Subjects must meet all of the following inclusion criteria to be eligible for participation in this study:

- 1) ≥ 18 years of age, female
- 2) Histologically or cytologically confirmed breast cancer with evidence of metastatic or locally advanced disease not amenable to resection or radiation therapy with curative intent and who have progressed during treatment with at least one prior hormonal therapy
 - a) Phase 1b Dose Escalation - Subjects may have had unlimited prior hormonal therapy and a total of 2 prior chemotherapy regimens (adjuvant chemotherapy is considered 1 regimen). Subjects may have progressed on fulvestrant or exemestane
 - b) Randomized Phase 2 Dose Expansion - Subjects may have disease progression during treatment or within 12 month of completion of endocrine therapy (tamoxifen, and/or AI) in the adjuvant setting, or disease progression during treatment with endocrine therapy (tamoxifen, AI or CDK4/6 inhibitor plus AI) for advanced/metastatic disease. Subjects may have had unlimited prior hormonal therapy, but must be naïve to fulvestrant in the metastatic setting. A total of 2 prior chemotherapies are allowed, however, only one for metastatic disease is permitted.
- 3) Documentation of ER positive breast cancer ($\geq 1\%$ positive stained cells by local standards) based on the most recent tumor biopsy, unless bone-only disease
- 4) Documented HER2-negative tumor based on local testing on most recent tumor biopsy (immunohistochemistry score 0/1+ or negative by in situ hybridization HER2/CP17 ratio < 2 or for single probe assessment HER2 copy number < 4)

- 5) Post, pre or peri-menopausal subjects considered to be in the post-menopausal state as defined by one of the following:
 - a) Age \geq 60 years
 - b) Age $<$ 60 years and cessation of regular menses for at least 12 consecutive months in the absence of chemotherapy, tamoxifen, toremifene, or ovarian suppression and serum estradiol and follicle-stimulating hormone (FSH) level within the post-menopausal range
 - c) Prior bilateral oophorectomy
 - d) Pre-/peri-menopausal women can be enrolled if amenable to be treated with the luteinizing-hormone releasing hormone (LHRH) agonist goserelin. Subjects must have commenced treatment with goserelin or an alternative LHRH agonist at least 4 weeks prior to C1D1. If subjects have received an alternative LHRH agonist prior to study entry, they must switch to goserelin on or before C1D1 for the duration of the study

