5.3. Dosage and Administration of GS-5829, Exemestane and Fulvestrant

GS-5829 tablets will be provided by Gilead Sciences, Inc. and will be taken orally. Initiation of treatment with the study drug will take place after enrollment and cohort assignment. Subjects will take their dose of study drug at approximately 24-hour intervals. Tablets should be taken whole, they should not be chewed or crushed. To reduce inter-subject variability on efficacy and safety, subjects will be instructed to take GS-5829 approximately 1 hour before or 2 hours after a meal. Grapefruit juice is prohibited while on study drug.

GS-5829 tablets will be self-administered orally once daily, beginning on C1D1 of the study and thereafter at approximately the same time each day until EOT.

For subjects in Group A (Phase 1b), exemestane 25 mg tablets will be self-administered orally once daily (or in accordance with locally approved labelling), beginning on C1D1 of the study and thereafter at approximately the same time each day until the EOT. Exemestane will be dispensed to subjects at visits on the first day of each cycle.

For subjects in Group B (Phase 1b) and in the Phase 2 Dose Expansion, fulvestrant will be administered intramuscularly (in accordance with locally approved labeling) by the clinic staff approximately every 28 days (\pm 3 days) until the EOT.

For subjects in the Randomized Phase 2 Dose Expansion phase and for subjects in Group B of the Phase 1b Dose Escalation whom are treatment naïve (in metastatic setting) and for all

subjects for whom C1D1 is the subject's first dose of fulvestrant, a one-time additional dose of 500 mg fulvestrant will be administered on C1D15 (\pm 3 days).

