6.3.3. Biomarker Samples for Optional Genomic Research

PPD

6.4. **Re-Screening Criteria**

Subjects who do not enroll within 28 days of screening will be screen failed.

Re-screening may be allowed. Subjects who are re-screened will be re-consented with new screening number, and will repeat the screening assessments. Subjects who do not meet QTc criteria are not allowed to re-screen (see Section 4.3). Gilead is to be informed prior to a subject re-screening.

6.5. **Treatment Assessments**

Each on-study visit will be scheduled relative to C1D1. Visits will follow the schedule of assessments in [Appendix 2](#) and [Appendix 3](#).

Subjects who meet eligibility criteria will receive GS-5829 orally once daily combined with daily orally dosing of exemestane (Group A Phase 1b) or injection of fulvestrant intramuscularly on Day 1, Day 28 and then every 28 days (\pm 3 days). Subjects initiating fulvestrant on C1D1 should receive a single additional dose at C1D15. Subjects in the Phase 1b Dose Escalation phase of the study may initiate exemestane (Group A) or fulvestrant (Group B) any time prior to, or on, C1D1. Each cycle will consist of 28 days. Safety and efficacy assessments will occur on an outpatient basis including an assessment of tumor response, physical exam, vitals, ECG, collection of blood samples (for routine safety labs, GS-5829 pharmacokinetic, pharmacodynamic markers, and biomarkers at applicable visits), and assessment of AEs. In addition, subjects will undergo a CT scan (or MRI) scan every 8 weeks for the first year and then every 12 weeks. Bone scans may be repeated as clinically indicated or to confirm a CR.

A subject who does not show evidence of disease progression may continue receiving GS-5829 once daily and exemestane (Group A Phase 1b) or fulvestrant until disease progression (clinical or radiographic), unacceptable toxicity, withdrawal of consent, or other reasons specified in Section 3.5. If a subject who is randomized to the combination arm discontinues one study drug for any reason, such as toxicity the other study drug will be discontinued as well.

6.6. **Post-treatment Assessments**

All subjects will complete the 30-Day Safety Follow-Up Visit (\pm 5 days). For Phase 1b Dose Escalation subjects, the 30-Day Safety Follow-Up will be the final study visit. Randomized Phase 2 Dose Expansion subjects will complete the 30-Day Safety Follow-Up Visit and proceed to Long Term Survival Follow-Up (LTFU) (See Section 6.7).

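### The protocol contradicts itself on which Phase 2 patients receive the Day 15 fulvestrant dose; at target stratum sizes this covers about half of each arm

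*Protocol*

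**What the plan says.** Several places in the protocol state who receives the one-time additional fulvestrant dose on Cycle 1 Day 15.

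- **Synopsis, Reference Therapy:** "For subjects in the dose expansion Phase whom are treatment naïve (in metastatic setting) and for all subjects in the dose escalation phase" whose first fulvestrant dose falls on C1D1. For Phase 2 the condition is being treatment naive in the metastatic setting. The first-fulvestrant-dose condition is attached to dose escalation.
- **Synopsis, Test Product:** one sentence covers Phase 1b and randomized Phase 2. It names patients who are treatment naive in the metastatic setting and then adds: "for all subjects for whom C1D1 is the subject's first dose of fulvestrant, a one-time additional dose of 500mg fulvestrant will be administered".
- **Section 5.3:** the population is introduced with "For subjects in the Randomized Phase 2 Dose Expansion phase and for subjects in Group B of the Phase 1b Dose Escalation", and the trigger includes "subjects for whom C1D1 is the subject's first dose of fulvestrant, a one-time additional dose of 500 mg fulvestrant will be administered on C1D15".
- **Section 6.5:** "Subjects initiating fulvestrant on C1D1 should receive a single additional dose at C1D15".
- **Appendix 2, administration row and footnote 12:** the Day 15 dose goes to those who start fulvestrant on the study. Neither mentions a treatment-naive condition.

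Three other provisions determine who is affected. Section 4.2, criterion 2b, admits patients with "disease progression during treatment with endocrine therapy (tamoxifen, AI or CDK4/6 inhibitor plus AI) for advanced/metastatic disease". Section 5.4 does not allow prior fulvestrant in Phase 2. Section 3.2 starts both drugs on C1D1 in Phase 2 and sets a target of about 60 patients per CDK4/6 stratum, 40 on the combination and 20 on fulvestrant alone.

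**The concern.** Fulvestrant is the background drug in both Phase 2 arms and the whole of the control regimen. The trial estimates the effect of adding GS-5829 to it, so the fulvestrant start has to be defined by a single rule. As written, a site reading the Reference Therapy paragraph and a site reading Section 5.3 would treat the same patient differently in Cycle 1.

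The patients on whom the texts disagree are not a random subset. They include essentially the whole CDK4/6-progressed stratum. Section 8.2.1.1 calls for a separate PFS analysis in each stratum, and Section 8.9 gives each stratum its own power statement. The background treatment in one of the two planned stratum comparisons is therefore undetermined by the protocol.

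There is also a smaller consequence. Section 8.6.1 measures fulvestrant compliance against the planned number of doses, and Section 8.2.1.2 makes the per-protocol set depend on treatment compliance. For the affected patients the planned number depends on which text is followed.

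**Working it through.** **1. The plan's own figures.** Inputs from Section 8.9: medians of 4 and 8 months (HR = 4/8 = 0.5), 2:1 allocation, one-sided alpha 0.1, 88 events in total and 44 per stratum. Schoenfeld's approximation gives

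power = Φ(|ln HR| × √(D × 2/3 × 1/3) − 1.2816).

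- D = 88: 0.6931 × √19.556 = 3.065; Φ(1.784) = 96.3%, against the stated figure of more than 90%.
- D = 44: 0.6931 × √9.778 = 2.167; Φ(0.886) = 81.2%, against the stated 80%.

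With exponential PFS, uniform 9-month accrual, 19 months in total and 10% drop-out by 12 months, expected events are 35.0 + 53.9 = 88.9, against 88 stated. The design figures reproduce, and nothing here changes them. They show that each stratum is planned as a comparison in its own right.

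**2. Apply each rule to the Phase 2 population.**

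| Patient group | Reference Therapy text | Test Product text, 5.3, 6.5, Appendix 2 |
|---|---|---|
| CDK4/6-progressed | Not covered: prior CDK4/6 inhibitor plus AI was for advanced/metastatic disease (criterion 2b) | Covered: first fulvestrant dose is C1D1 (Sections 3.2 and 5.4) |
| CDK4/6-naive, earlier endocrine therapy for metastatic disease | Not covered | Covered |
| CDK4/6-naive, no earlier treatment for metastatic disease | Covered | Covered |

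**3. Count the patients on whom the rules disagree.** At target the progressed stratum holds 20 controls and 40 combination patients:

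- controls: 20/40 = 50%
- combination: 40/80 = 50%
- overall: 60/120 = 50%

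**4. Add the naive stratum.** Let f be the fraction of CDK4/6-naive patients already treated for metastatic disease. The documents give no value for f, so it is an assumption and the full range is shown. Affected controls = 20 + 20f; affected combination patients = 40 + 40f.

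| f | Controls | Combination | Share of each arm |
|---|---|---|---|
| 0 | 20 | 40 | 50% |
| 0.5 | 30 | 60 | 75% |
| 1 | 40 | 80 | 100% |

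**5. Allow for drift from target.** The stratum sizes are approximate. If the progressed stratum were 40% to 60% of enrolment, its control count alone would be 0.4 × 40 = 16 to 0.6 × 40 = 24. One half is therefore the figure at target and not a guaranteed minimum.

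**The case against.** **The arms are not treated differently.** A reader might infer that controls follow the Reference Therapy paragraph while combination patients follow the Test Product paragraph, so that the PFS difference mixes GS-5829 with a different fulvestrant start. The documents do not support this. The Reference Therapy sentence speaks of the dose expansion phase, not of controls. The Test Product text names Arm 2, the control arm, in its sentence on four-weekly fulvestrant, and its Day 15 sentence covers Phase 2 without splitting by arm. Section 5.3 names all of Phase 2. In footnote 12 of Appendix 2 the four-weekly sentence is about fulvestrant given with GS-5829, but the Day 15 sentence carries no such limit. A between-arm difference would need sites to apply each synopsis heading to its own arm. The open-label design makes that possible, but no text directs it. This objection stands.

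**One synopsis sentence is out of line with the rest.** That is a fair description and suggests a drafting slip. It does not settle which rule was intended, and the sentence sits where a reader would look up the control regimen.

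**Treatment naive may mean fulvestrant naive.** Eligibility uses similar words about fulvestrant, and on that reading every Phase 2 patient would qualify. But the Test Product text lists being treatment naive and having a first fulvestrant dose on C1D1 as separate conditions, so the protocol itself distinguishes them. The phrase is undefined, and this reading does not remove the conflict.

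**Phase 2 never ran.** Correct. SAP Section 1 records that the study stopped during dose escalation. This limits urgency but does not make the text consistent.

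**Conclusion.** The contradiction is real. The Reference Therapy paragraph defines a narrower Phase 2 group for the Day 15 dose than the synopsis Test Product text, Sections 5.3 and 6.5, and Appendix 2. At the approximate stratum targets the conflict covers about half of each arm (20 of 40 controls and 40 of 80 combination patients), rising towards the whole of each arm as f increases. It covers essentially all of the CDK4/6-progressed stratum.

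The proportion affected is the same in both arms, so these figures count patients with conflicting instructions. They do not measure imbalance or bias in PFS, and no effect on PFS can be estimated from the documents.

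The conclusion rests on three assumptions:

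- Treatment naive in the metastatic setting is read as no earlier treatment for metastatic disease.
- Prior CDK4/6 inhibitor plus AI was given for advanced or metastatic disease, as criterion 2b lists it.
- No Phase 2 patient has had fulvestrant, as Section 5.4 states. Section 4.2 is looser and bars it only in the metastatic setting, so a patient given fulvestrant earlier would be an exception to the statement that all meet the wider rule.

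No patient was randomized, so no collected data are affected. No view is taken on which dosing rule is right.

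**What to change.** Reconcile the synopsis Reference Therapy and Test Product texts, Section 5.3, Section 6.5, and the Appendix 2 administration row and footnote 12 into one statement of who receives the Day 15 fulvestrant dose. State that it applies identically to both Phase 2 arms. Define treatment naive in the metastatic setting if the phrase is kept, and check Section 3.3, which also uses the first-dose trigger, against the result. Which rule is right is for the sponsor to decide.

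The cost is a wording correction, with no change to sample size, power or analysis. Because Phase 2 was not started, its value lies in the accuracy of the plan text and in any later protocol that reuses it.

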1. INTRODUCTION

1.1. Background

GS-5829 is a small-molecule inhibitor of the highly conserved bromodomain pockets of the bromodomain and extraterminal (BET) proteins. Bromodomain and extraterminal proteins regulate specific gene expression by enhancing ribonucleic acid (RNA) polymerase II (RNAPII) mediated transcription. Signal transduction pathways recruit BET proteins to target genes through posttranslational modification of histone proteins in the form of lysine acetylation {Belkina 2012, Hargreaves 2009}. The tandem bromodomain motifs of BET proteins specifically recognize acetylated histones and, in turn, recruit protein factors that regulate RNAPII {Shi 2014}. The BET family includes bromodomain-containing proteins 2, 3, 4, and T (BRD2, 3, 4, and T). BRD2, 3 and 4 are widely expressed and regulate gene transcription in diverse cell types, including malignant cells, whereas BRDT expression is restricted to the testes.

BRD2, 3, 4 are essential regulators of the expression or activity of several key oncogenic transcription factors, including v MYC avian myelocytomatisis viral oncogene homolog (MYC) and the androgen receptor (AR) {Shi 2014}. Transcription of the MYC gene is dependent on BET proteins in many cells {Mertz 2011}. Androgen receptor-dependent transcription of target genes requires BET proteins in prostate cancer cells {Asangani 2014}. Cancer cells addicted to MYC and AR are highly sensitive to BET protein inhibition {Asangani 2014, Delmore 2011, Mertz 2011}, which provides the basic therapeutic rationale for BET inhibition with GS-5829 for the treatment of cancer.

MYC promotes cell proliferation, cell survival, and metabolic adaptation and is frequently overexpressed in human cancers {Dang 2012}. Data generated at Gilead demonstrated MYC overexpression to be prevalent in 76% of prostate cancer (n = 60), 67% of diffuse large B-cell lymphoma (DLBCL) (n = 98), 65% of multiple myeloma (MM, n=30), 73% of colorectal cancer (n = 60), and 80% of ovarian cancer (n = 60) cases examined (PC-350-2083). These data are consistent with literature that reports a high incidence of MYC expression in these and other cancers {Affer 2014, Barrans 2010, Chesi 2008, Chng 2011, Glitza 2014, Hawksworth 2010, Nesbit 1999, Nupponen 1998, Perry 2014}. The AR is a nuclear hormone receptor that is nearly ubiquitously expressed in prostate cancer (PC-350-2083) and activates growth and survival signals both by binding to androgen, its natural ligand, and through androgen-independent mechanisms {Yuan 2014}.

A number of orally administered, BET-directed compounds (TEN-010, CPI-0610, OTX015, ZEN-3365, and GSK525762) are currently in early-stage clinical development for the treatment of solid tumors or hematologic cancers {Filippakopoulos 2014, Ghoshal 2016}. Initial evidence of clinical activity at tolerated doses has been reported for the BET inhibitor OTX015 in subjects with refractory hematological cancers {Amorim 2016, Berthon 2016}. GS-5829 is an orally available small-molecule inhibitor of BET proteins that is being developed by Gilead Sciences, Inc. for the treatment of solid tumors, including castrate-resistant prostate cancer (CRPC), estrogen receptor-positive (ER+)/human epidermal growth factor receptor 2-negative (HER2-) breast cancer (BrCa) (ER+/HER2- BrCa), and hematologic malignancies. In nonclinical studies,

GS-5829 inhibited cell growth and induced apoptosis of solid tumor and hematological cancer cells by inhibiting BET protein-dependent transcription of MYC and other oncogenic pathways, including transcription mediated by the AR in prostate cancer cells.

